Sample Size: The sample size is based on the comparison of each dose level of ifetroban (Low Dose or High Dose) to placebo with respect to change from baseline in LVEF using CMR for each disease stage, early (LVEF > 45%) or advanced (current/historical LVEF 35% - 45%). Assuming observations from each treatment group have normal distributions with an effect size of 1.6 for the comparison of a dose of ifetroban to placebo, 8 subjects for each treatment group within disease stage will provide power exceeding 85% for a t-test at two-sided level 0.05. Under these assumptions, 8 subjects for each treatment group within disease stage will provide power exceeding 80% for the Wilcoxon rank sum test at two-sided level 0.05. A total of 48 DMD subjects will be enrolled: 24 subjects with early stage DMD (LVEF > 45%) and 24 with advance stage DMD (current/historical LVEF 35%-45%). Assuming a dropout rate of 25%, 60 subjects will be recruited to meet the target sample size of 48 subjects.		

Name of Sponsor:	Name of Finished Product:	Name of Active Ingredient:
Cumberland Pharmaceuticals	Ifetroban Capsules	ifetroban
Enrollment:		
Subjects will be randomly assigned to one of three oral treatment groups: low-dose ifetroban, high-dose ifetroban or placebo for 12 months based on weight within each disease stage, early (LVEF > 45%) or advance (current/historical LVEF 35%-45%).		
Low Dose: < 35 kg: 50 mg, ≥ 35 kg: 100 mg/day		
High Dose: < 35 kg: 150 mg, ≥ 35 kg: 300 mg/day		
Analysis Population:		
All subjects who receive at least one dose of study medication will be included in the Safety Population. All safety data will be summarized for subjects in the Safety Population.		
The Intent-To-Treat (ITT) Population will consist of all treated subjects with at least one post-baseline assessment. The Per Protocol (PP) Population will consist of all subjects in the ITT population with no major protocol violations, including violation of inclusion or exclusion criteria or insufficient dosing where the latter includes missing more than 2 consecutive weeks of dosing for any reason or missing >20% of prescribed doses between visits. Summary statistics will be presented for both the ITT and PP Populations.		
Interim Analysis:		
An early analysis will be performed when half the target enrollment has completed the six month visit and assessments. Key findings for the interim analysis will be summarized.		
Historical Comparator Analyses:		

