11.6 Randomization

Subjects will be randomly assigned to one of three treatment groups: low-dose ifetroban, high-dose ifetroban, placebo, using a 1:1:1 randomization ratio. All subjects will be treated with IMP daily for at a minimum of six months and a maximum of 12 months.

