11.8.3 Efficacy Analyses

Between-treatment comparisons with respect to the change from baseline in LVEF and the change from baseline in myocardial strain at Month 6 and Month 12 will be performed for the ITT and PP Populations using the Wilcoxon rank sum test. A supportive analysis with missing LVEF at Month 12 imputed by LVEF at Month 6; subjects missing LVEF at both Month 6 and Month 12 will be excluded from this supportive analysis. In line with the current paradigm for the assessment of therapeutic efficacy in rare diseases and specifically DMD using established natural history data ([Liu 2022](#), [US FDA 2019](#), [US FDA 2018](#)), a comparison of the NHS-supplemented placebo group (2:1 NHS to placebo) will also be performed at Month 12 versus the high-dose ifetroban ITT and PP populations for CMR parameters.

Summary statistics for other endpoints will be presented for both the ITT and PP Populations.

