### **3.4 Sample Size**

The sample size is based on the comparison of each dose level of ifetroban (Low-Dose or High-Dose) to placebo with respect to change from baseline in LVEF using CMR for each disease stage, early (LVEF > 45%) or advanced (LVEF 35-45%).

Assuming observations from each treatment group have normal distributions with an effect size of 1.6 for the comparison of a dose of ifetroban to placebo, 8 subjects for each treatment group within disease stage will provide power exceeding 85% for a t-test at two-sided level 0.05. Under these assumptions, 8 subjects for each treatment group within disease stage will provide power exceeding 80% for the Wilcoxon rank sum test at two-sided level 0.05.

A total of 48 DMD subjects will be enrolled: 24 subjects with early stage DMD (LVEF > 45%) and 24 with advance stage DMD (LVEF 35-45%). Assuming a dropout rate of 10%, 54 subjects will be recruited to meet the target sample size of 48 subjects.

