### **3.5 Randomization**

Subjects will be randomly assigned to one of three treatment groups: low-dose ifetroban 100 mg/day, high-dose ifetroban 300 mg/day or matching placebo, using a 1:1:1 randomization ratio. All subjects will be treated with IMP daily for a minimum of six months and a maximum of 12 months. Approximately 48 subjects shall be randomized to ensure at least 16 subjects per group will be analyzed for efficacy.

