### 6.2.1 Change from baseline in LVEF and Myocardial Strain using CMR

The secondary analysis will focus on the change from baseline in LVEF and myocardial strain over 12 months of dosing.

The change from baseline in LVEF and myocardial strain will be compared between the treatment groups (High-Dose Ifetroban vs Placebo; Low-Dose Ifetroban vs Placebo) using Wilcoxon rank sum test for ITT population.

The number and change from baseline in LVEF and myocardial strain for each treatment group and overall, in the ITT population will be summarized descriptively. The following myocardial strain endpoints will be summarized:

- Indexed left ventricular end diastolic volume (LVEDVi)
  - LVEDVi = LVEDV/body surface area (BSA)
  - BSA calculation from CMR dataset using the Haycock method for pediatrics =  $0.024265 \times (\text{ht\_cmr})^{0.3964} \times (\text{wt\_cmr})^{0.5378}$
  - From CMR dataset: LVEDVi = “lvedv\_cmr”/ “bsa\_calc\_cmr”
- Indexed left ventricular end systolic volume (LVESVi)
  - LVESVi = LVESV/body surface area
  - BSA calculation from CMR dataset using the Haycock method for pediatrics =  $0.024265 \times (\text{ht\_cmr})^{0.3964} \times (\text{wt\_cmr})^{0.5378}$
  - From CMR dataset: LVESVi = “lvesv\_cmr”/ “bsa\_calc\_cmr”
- Mid Ecc (circumferential strain)

- Global Ecc
- Late gadolinium enhancement, full-width half-maximum (LGE FWHM)
- Number of segments with LGE (number of LGE segments with values >0)
- Base T1
- Mid T1

A subject data listing of all LVEF and myocardial strain will be provided.

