## 6.5 Subgroup Analyses

To assess the consistency of treatment effects across the subgroup levels, and to examine baseline biomarkers for their potential value to predict treatment response, exploratory subgroup analyses will be conducted for safety, tolerability, pharmacokinetics, and efficacy for the variables below.

The following subgroups will be assessed using the primary endpoint and primary endpoint related to clinical assessments, secondary endpoints, and exploratory endpoints.

- DMD disease stage (Early LVEF>45%, Late LVEF 35%-45%)
- Ambulation status (ambulatory vs non-ambulatory)
- Background therapy (none, steroids, ASO, steroids + ASO)

For each subgroup analysis, results will be presented as stratified analyses with descriptive statistics and treatment effect estimates within each subgroup level. Forest plots will be used to display treatment effects across subgroup levels for key endpoints. No formal statistical testing for interaction between subgroup and treatment will be performed due to limited sample sizes within subgroups, but the consistency of treatment effects across subgroup levels will be evaluated qualitatively. These analyses are considered exploratory and intended to identify potential patterns that may inform future research rather than to draw definitive conclusions about differential treatment effects.

Missing data in each factor, which will be limited if any, will not be included (as a separate group) in subgroup analyses. This does not apply to the PSM analysis.

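### The LVEF and strain tests between randomised arms ignore disease stage, although the trial is sized within stage and the SAP's stage definition omits the protocol's historical-LVEF route

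*SAP*

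**What the plan says.** **Sizing.** Protocol 11.1 and SAP 3.4 base the sample size on each dose against placebo within each stage. For an effect size of 1.6 they claim power above 85% for a t-test, and SAP 3.4 adds that "8 subjects for each treatment group within disease stage will provide power exceeding 80% for the Wilcoxon rank sum test at two-sided level 0.05". Protocol Table 7-1 sets out the same 8 per arm per stage.

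**Assignment.** The protocol synopsis assigns subjects "for 12 months based on weight within each disease stage, early (LVEF > 45%) or advance (current/historical LVEF 35%-45" per cent). Protocol 11.6 says only "Subjects will be randomly assigned to one of three treatment groups: low-dose ifetroban, high-dose ifetroban, placebo, using a 1:1:1 randomization ratio", and SAP 3.5 likewise "or matching placebo, using a 1:1:1 randomization ratio". Neither randomisation section names strata.

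**Tests.** Under SAP 6.2.1, change in LVEF and strain "will be compared between the treatment groups (High-Dose Ifetroban vs Placebo; Low-Dose Ifetroban vs Placebo) using Wilcoxon rank sum test for ITT population". In protocol 11.8.3 the comparisons at Months 6 and 12 "will be performed for the ITT and PP Populations using the Wilcoxon rank sum test". Neither mentions stage.

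**Stage in the analysis.** SAP 6.5 lists "DMD disease stage (Early LVEF>45%, Late LVEF 35%-45" per cent) as an exploratory subgroup, where "results will be presented as stratified analyses with descriptive statistics and treatment effect estimates within each subgroup level". It adds forest plots, names no within-stage test and rules out interaction tests.

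**Definition of late stage.** Protocol 7.3.1, criterion 3a, admits to the late cohort either a current LVEF of 35-45%, or a historical LVEF of 35-45% with a baseline below 50%. The SAP uses only 35-45% against above 45% wherever it defines stage (3.1, 3.4, 5.2, 5.5, 6.3.1, 6.5). SAP 4.4.4 and section 8 declare no changes from the protocol.

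**The concern.** The power statement and the planned tests describe different comparisons. A reader who asks which test has the stated power finds none.

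Stage is built into the design because early and late disease are expected to behave differently. If 12-month change in LVEF does differ by stage, that difference enters the pooled test as noise. If allocation was not stratified, a chance excess of late-stage subjects in one arm can also shift the pooled comparison in the trial actually run.

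The definition gap is a separate problem. A subject enrolled in the late cohort through the historical route, with baseline LVEF above 45% and below 50%, falls under Early if the SAP's cut-offs are applied to baseline LVEF. The SAP does not say whether stage means the enrolled cohort or is re-derived, and SAP section 10 places the derivation rules in separate documents. Stage tables may therefore not match the enrolled 24/24 cohorts.

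**Working it through.** **1. The plan's own figure.** Inputs from protocol 11.1 and SAP 3.4: effect d = 1.6 SD, n = 8 per arm, two-sided 0.05.
- t-test: df = 14, noncentrality = 1.6 × √(8/2) = 3.2, power 84.5%. This is half a point under the stated 85%; a normal approximation gives 89.3%.
- Exact Wilcoxon: reject if U ≤ 13 or U ≥ 64 − 13 = 51 (size 4.99%). Power is 82.5% at d = 1.6, 44% at 1.0 and 30% at 0.8.

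The stated power is thus essentially right, but for 8 vs 8 tests. The test in SAP 6.2.1 compares 16 with 16.

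**2. Why pooling can cost power.** The pooled test assumes a null variance for U of 16 × 16 × 33/12 = 704. If the stages did not overlap at all, only within-stage comparisons would vary, and the variance would be 2 × (8 × 8 × 17/12) = 181.3. The test would then use a standard deviation √(704/181.3) ≈ 2 times too large. Partial separation gives a partial version of this.

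**3. Pooled against stratified, balanced stages.** Normal data, 8 per arm per stage, 40,000 simulated trials per scenario (Monte Carlo SE at most √(0.25/40,000) = 0.25 points). The pooled Wilcoxon uses the continuity-corrected normal approximation. Van Elteren sums U/(N+1) over stages, where N is the number of subjects in both arms of that stage. The stage difference in mean 12-month change is an assumed range in within-stage SD. Entries are percentages of trials that reject.

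| True effect (SD) | Pooled, stage difference 0 / 0.5 / 1 / 1.5 | Stratified, all stage differences |
|---|---|---|
| 1.6 | 98.9 / 98.5 / 97.4 / 95.0 | 98.5-98.7 |
| 1.0 | 75 / 73 / 66 / 54 | 74 |
| 0.8 | 56 / 53 / 45 / 34 | 55 |
| 0 (type I error) | 4.9 / 4.0 / 2.7 / 1.2 | 4.7-4.9 |

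**4. Effect in one stage only.** With an effect of 1.6 in early disease and none in late disease (exact critical values, 60,000 simulations), the pooled test has 41.8% power with no stage difference and 19.0% at 1 SD. Van Elteren has about 41% in both cases. The within-stage test keeps 82%. Stratification alone therefore does not answer the question the trial was sized on.

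**5. If allocation was not stratified.** Take 24 early and 24 late subjects permuted into three arms of 16. The late-stage count in an arm has variance 16 × 0.25 × 32/47 = 2.72, and the covariance between two arms is −16 × 16 × 0.25/47 = −1.36. Their difference has variance 2 × (2.72 + 1.36) ≈ 8.2, SD 2.86. A difference of 4 or more has probability about 2 × [1 − Φ(3.5/2.86)] = 22%, as in simulation. In those allocations, pooled type I error is 6.2 / 8.6 / 13.0% at stage differences of 0.5 / 1 / 1.5 SD, against 4.6-5.2% stratified. Repeat simulations move these by up to 0.7 points, so read them as about 6, 9 and 13%. Over all allocations the pooled error stays at 4.4-4.9%.

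**6. Stage definition, side by side.** A subject with historical LVEF 40% and baseline LVEF 47% is eligible for the late cohort under protocol 3a (historical 35-45%, baseline below 50%). By the SAP cut-offs applied to baseline, 47% is above 45%, so the subject is Early. The documents do not say how many subjects this affects.

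**The case against.** **The harm is small on the plan's own terms.** At an effect of 1.6 the pooled test still has 95.0% power or more over the assumed range, well above the 82.5-84.5% of the 8 vs 8 tests. The large losses need both a smaller effect and a stage difference of 1 SD or more, and the documents support neither. LVEF and strain are secondary endpoints in a trial whose primary endpoint is safety. All of this is correct, and it limits the weight of the power argument.

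**Allocation was probably by stage.** The synopsis says so, and fixed cells of eight imply it. The randomisation sections are silent rather than contradictory. The raised error in step 5 is also conditional on the more imbalanced allocations. This stands too, so step 5 is secondary. But if stage was used in assignment, that is itself a reason to use it in the test.

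**A late change has a price.** Protocol 14.2 requires an amendment with IRB approval for substantive changes, and SAP 4.3 reports the interim analysis as done, so replacing a test now could look data-driven. The answer is to date the change, give a design-based reason and document it openly.

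**The SAP's cut-offs may be shorthand.** The SAP says it follows the current protocol, and the protocol's labels overlap too, since early is simply LVEF above 45%. That is possible, but the SAP does not say so, and the overlap makes an explicit rule more necessary.

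**Conclusion.** The concern holds. Three points need no assumption: the stated power belongs to within-stage tests that are not planned; the synopsis and the randomisation sections differ on whether stage governed assignment; and the SAP omits one of the protocol's two routes into the late cohort.

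The size of the power loss does rest on assumptions: normal data, 8 per arm per stage, the same effect in both stages, and an assumed stage difference in 12-month change. It is 0-4 points at the plan's effect of 1.6. At effects of 0.8-1.0 it is 1-2 points for a 0.5 SD stage difference and 8-21 points for 1-1.5 SD. With balanced stages the pooled test does not inflate type I error; it becomes conservative. This should be corrected, but it does not invalidate the trial.

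**What to change.** 1. In SAP 6.2.1 and protocol 11.8.3, replace the pooled Wilcoxon test with a van Elteren test of each dose against placebo, stratified by the disease-stage cohort in which the subject was enrolled. Record the change and its reason in SAP section 8. The pooled test can be kept as supportive.
2. Either add the within-cohort Wilcoxon tests to which the power statement refers, or restate the power for the stratified 16 vs 16 test.
3. Define Early and Late once in the SAP by enrolled cohort, with Late covering both routes of protocol criterion 3a. Use that definition in 3.1, 3.4, 5.2, 5.5, 6.3.1 and 6.5.
4. Reconcile protocol 11.6 and SAP 3.5 with the synopsis by stating whether stage was a randomisation stratum.

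The analysis work is SAP wording and one SAS option (the CMH row-mean-score test with modified ridit scores). The protocol edits carry the usual amendment effort. The statistical price is about 1 point of power or less if stage does not matter: 54.8% against 55.7% at effect 0.8, and 98.7% against 98.9% at 1.6.

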### **6.2.2 Interobserver Variability**

CMR images are reviewed by a primary internal reviewer and a secondary external reviewer to assess interobserver variability. The intraclass correlation coefficient (ICC) will be calculated to evaluate consistency between reviewers using a two-way mixed effects model where reviewers are treated as fixed effects and subjects as random effects.

ICC will be calculated as follows:

$$\text{ICC} = (\text{MSR} - \text{MSE}) / [\text{MSR} + (k-1) * \text{MSE}]$$

where MSR is the mean square for rows, MSE is the mean square error, and k is the number of reviewers.

The 95% confidence intervals for ICC values will be estimated using bootstrapping with 1000 resamples. P-values for agreement between observers will be tested using likelihood ratio tests comparing models with and without the reviewer effect.

ICC values will be interpreted as follows:

- < 0.5: Poor reliability
- 0.5 to 0.75: Moderate reliability
- 0.75 to 0.9: Good reliability
- > 0.9: Excellent reliability

ICC values along with 95% confidence intervals and p-values will be calculated for each CMR parameter at each visit and overall by treatment group.

### **6.2.3 Change from baseline in Pulmonary Function Test**

The secondary analysis will focus on the change from baseline (see [Section 4.4.1](#) for definition) in Pulmonary function test over 12 months of dosing.

The change from baseline in PFT will be assessed by the following efficacy variables:

- Forced Expiratory Volume 1 (FEV1)
  - FEV1 Value = Collected on the CRF. Measured as the “best effort” of the 3 collected measurements at each time point where “best effort” = Max (FEV1\_1, FEV1\_2, FEV1\_3)
  - FEV1 percent predicted (FEV1%p) = Collected on CRF. Calculated from subject metrics and measured FEV1 values.
  - CFB FEV1 = post-treatment measurement – baseline
  - CFB FEV1%p = post-treatment measurement – baseline
- Forced Vital Capacity in liters (FVC)
  - FVC Value = Collected on the CRF. Measured as the “best effort” of the 3 collected measurements at each time point where “best effort” = Max (Fvc\_1, Fvc\_2, Fvc\_3)
  - FVC percent predicted (FVC%p) = Collected on CRF. Calculated from subject metrics and measured FVC values.
  - CFB FVC = post-treatment measurement – baseline
  - CFB FVC%p = post-treatment measurement – baseline
- Maximal Expiratory Pressure in cm of water (MEP)
  - MEP Value = Collected on the CRF. Measured as the “best effort” of the 3 collected measurements at each time point where “best effort” = Max (MEP\_1, MEP\_2, MEP\_3)
  - CFB MEP = post-treatment measurement – baseline
- Maximal Inspiratory Pressure in cm of water (MIP)
  - MIP Value = Collected on the CRF. Measured as the absolute value of the “best effort” of the 3 collected measurements at each time point where “best effort” = Max (MIP\_1, MIP\_2, MIP\_3).
  - CFB MIP = post-treatment measurement – baseline
- Peak Expiratory Flow rate in liters/second (PEF)

- PEF Value = Collected on the CRF. Measured as the “best effort” of the 3 collected measurements at each time point where “best effort” = Max (PEF\_1, PEF\_2, PEF\_3)
- PEF percent predicted (PEF%p) = Collected on CRF. Calculated from subject metrics and measured PEF values.
- CFB PEF= post-treatment measurement – baseline
- CFB PEF%p= post-treatment measurement – baseline

The number and change from baseline in PFT for each treatment group and overall, in the ITT population will be summarized descriptively.

A subject data listing of all PFT will be provided.

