#### 9.1.1 Pulmonary Function Test

Three sets of observations are measured for each variable in PFT. The “best” of the 3 values to be flagged according to the following procedure:

**STEP 1:** Order the 3 values to low, middle, high

**STEP2:** Calculate the % difference between the middle and the high value.

$$\% \text{difference} = (\text{high} - \text{middle}) / \text{high}$$

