#### STEP3:

if the %difference is  $\leq 10\%$  then flag the high value as the best value

If the %difference is  $> 10\%$  then flag the middle value as the best value

The **low** value will never be used.

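### MIP is the absolute value of the maximum of three efforts; if pressures are stored as negative numbers, that rule and SAP 9.1.1 both select the weakest effort

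*SAP*

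**What the plan says.** SAP 6.2.3 gives the MIP value as "Measured as the absolute value of the" best of the three efforts at a visit, and defines that best effort as the maximum of MIP_1, MIP_2 and MIP_3. The order of operations is therefore abs(Max(...)). FEV1, FVC, MEP and PEF use the same maximum rule with no absolute value. The endpoint is a plain difference: "CFB MIP = post-treatment measurement – baseline".

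SAP 9.1.1 gives a second rule for choosing the best of three, covering every pulmonary function variable. Step 1 is "Order the 3 values to low, middle, high". Step 2 divides the gap between high and middle by high. Step 3 takes the high value if that ratio is at most 10%; otherwise the instruction is "then flag the middle value as the best value". The low value is excluded in all cases. There is no absolute-value step.

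Both the protocol (6.5) and the SAP (3.3.2) list MIP among the pulmonary function results that form a secondary efficacy endpoint. SAP 6.2.3 gives the unit, cm of water. Neither document says whether MIP is entered on the CRF as a positive or a negative number.

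**The concern.** Inspiratory pressure is a suction pressure and can be recorded with a minus sign. Applying an absolute value to MIP alone suggests that the SAP's authors had this in mind. If so, the operations are in the wrong order. Among negative numbers the maximum is the one nearest zero, so the written formula returns the weakest effort and then drops its sign. The 9.1.1 steps do not repair this, because they too order the signed values.

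At stake is whether the MIP summaries describe the best effort, as the SAP intends, or the worst. A change of sign between two visits of the same subject would also enter the change score as if it were a change in muscle strength.

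**Working it through.** The SAP states no figure to reproduce here; the check applies its two rules as written. The pressures, the true MIP of 60 cmH2O, the 10% decline and the within-session CVs are illustrative assumptions, because the documents give none.

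**1. One triplet, stored as negative: -60, -55, -48.**
- 6.2.3: Max = -48, absolute value 48. The strongest effort is 60. Shortfall (60 - 48)/60 = 20%.
- 9.1.1: low = -60, middle = -55, high = -48. Ratio = (-48 + 55)/(-48) = 7/(-48) = -14.6%. This is not above 10%, so -48 is flagged. The strongest effort is the low value, which the rule never uses.
- Absolute values first: 6.2.3 gives 60. In 9.1.1 the ratio is (60 - 55)/60 = 8.3%, so 60 is flagged.

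**2. The 9.1.1 result is general.** For three negative values, high - middle is zero or positive and high is negative, so the ratio is zero or negative. The switch to the middle value can never occur. In simulated all-negative triplets the high value, which is the weakest effort, was flagged every time.

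**3. The same triplet stored as positive: 60, 55, 48.** Max = 60, and the absolute value changes nothing. There is no error.

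**4. Size of the error in level, all entries negative.** For three independent normal efforts with mean 60, the simulated results are:

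| Within-session CV | Mean strongest | Mean weakest | Gap (cmH2O) | Mean shortfall per triplet |
|---|---|---|---|---|
| 5% | 62.5 | 57.5 | 5.1 | 8.0% |
| 10% | 65.1 | 54.9 | 10.1 | 15.3% |
| 15% | 67.6 | 52.4 | 15.2 | 22.1% |
| 20% | 70.2 | 49.9 | 20.3 | 28.3% |

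**5. Size of the error in the endpoint, all entries negative at every visit.** For a true decline from 60 to 54 with the same CV at both visits, the mean change is:

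| CV | Strongest effort used | Weakest effort used | Attenuation (cmH2O) |
|---|---|---|---|
| 5% | about -6.2 | about -5.7 | about 0.5 |
| 10% | -6.5 | -5.5 | about 1.0 |
| 15% | -6.8 | -5.2 | about 1.5 |
| 20% | -7.0 | -5.0 | about 2.0 |

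The proportional change in the means is -10% under either selection, and the standard deviation of the change is practically the same.

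**6. Sign switch within a subject.** If the efforts in step 1 are entered as negative at baseline and identical efforts are entered as positive at Month 12, 6.2.3 gives 48 and then 60. That is an apparent gain of 12 cmH2O with no change in strength.

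**7. The two rules against each other, whatever the sign.** For 40, 50, 60 (positive), 6.2.3 gives 60. In 9.1.1 the ratio is (60 - 50)/60 = 16.7%, above 10%, so it gives 50. Under the model in step 4 the top two efforts differ by more than 10% in about 5%, 30%, 47% and 58% of triplets at the four CVs.

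**The case against.** The strongest reply is that the fault depends on a sign convention that neither document shows. SAP section 10 places programming derivations and dataset specifications in separate documents, where sign handling may be settled. The absolute value may be only a safeguard. The intent is also clear from the words: for a maximal pressure, best effort means the largest in magnitude, and a careful programmer would code it so. This stands as a limit on the finding, which is conditional. It does not remove it: the SAP defines best effort by an explicit formula, and that formula is what a programmer or an independent checker would code.

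A second reply is that 8% to 28% is the wrong yardstick for the endpoint. A reader might infer that MIP results would be wrong by that much. They would not: those figures are shortfalls in level at one visit, whereas the endpoint is a within-subject change in which most of the level error cancels. The benchmark also matters. Against the value that 9.1.1 would select from positive entries, the level shortfall is about 7%, 11%, 15% and 18%. This reply stands.

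A third concerns mixed signs. A reader might infer that sites using different conventions would create artefactual changes. They would not if each subject's convention is the same at all visits. Only a switch within a subject does that, and nothing in the documents indicates that such switches occur.

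Finally, PFT data are listed by subject, so a wrong selection could be noticed.

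**Conclusion.** The rule is wrong as written for negative entries, and the MIP-only absolute-value step shows that the SAP allows for them. Both 6.2.3 and 9.1.1 then return the weakest effort. The documents do not support the stronger statement that the trial will analyse the weakest effort, because the sign convention is not given and all-positive data would be unaffected.

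Under all-negative recording, independent normal efforts and a within-session CV of 5% to 20%, the level at each visit is understated by about 8% to 28% against the strongest effort. The mean change is attenuated by about 0.5 to 2 cmH2O for a 10% decline from 60 cmH2O. A sign switch within a subject could produce a larger false change, 12 cmH2O in the example.

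The consequence for the trial is limited. MIP is one of five pulmonary function measures within one secondary endpoint, and 6.2.3 plans only descriptive summaries of it. The sample size rests on LVEF, so power and alpha are unaffected. The correction should still be made, since the formula contradicts its own stated aim and is easy to put right.

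**What to change.** In SAP 6.2.3, define the MIP value as Max(|MIP_1|, |MIP_2|, |MIP_3|). In SAP 9.1.1, state that MIP efforts are converted to absolute values before Steps 1 to 3. State the CRF sign convention in the SAP or in the derivation specification.

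In the same edit, keep one best-value rule. Correcting the sign in both sections still leaves 40, 50, 60 giving 60 under 6.2.3 and 50 under 9.1.1, and this conflict affects every pulmonary function variable to which both rules apply.

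The sign correction costs one line of SAP text and one of code, and changes nothing if all entries are positive. Choosing between the two rules needs a short decision by the sponsor. Both are best settled before database lock.
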